### 308 **Study Population:**

#### 309 Inclusion Criteria:

- 310 1. Informed consent obtained before any trial-related activities;
- 311 2. Both genders and all ethnicities;
- 312 3. Currently receiving medical care at Parkland Health and Hospital System (PHHS),  
313 Dallas, TX;
- 314 3. Age  $\geq$  18 years;
- 315 4. Diagnosis of Type-2 Diabetes, regardless of time since diagnosis;
- 316 5. Confirmed HbA1c  $>10\%$ .

317

318

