### 364 **Rationale for Study Location**

365 Only patients from the PHHS system will be recruited. PHHS is a county hospital that  
366 provides comprehensive care (primary, specialty, inpatient and outpatient) to the indigent  
367 population of Dallas County. EPIC is the electronic medical record that is deployed at all  
368 sites and covers all aspects of care, including financial data. Therefore PHHS is the ideal  
369 location to conduct this study, as all patient-related information is captured and can be  
370 queried at multiple levels, including cost.  
371

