- 554 missed or if the participant voices concern.

555

556 **Other Assessments**

557 Treatment satisfaction and quality of life will be assessed at the randomization visit (Visit

558 2) and end of study (Visit 6) using a modified DQoL and SF-36 questionnaires. Total

559 score as well as individual domain scores will be analysed and reported.

560

561 Subject Compliance: Participants will bring all study medication to each appointment for

562 review and study drug will be distributed at each appointment (visit 1, 2, 3, 4, and 5).

563 Percent compliance will be calculated and recorded at each visit.

564

565 Healthcare Cost Assessment: At the conclusion of the study, the EPIC integrated medical  
566 record system will be queried for the data regarding all healthcare related expenditures.  
567 From this information a data subset of diabetes-related expenditure will also be reported.

568

569 Physician Time Assessment: Each physician interaction (office visit or phone visit) will  
570 be timed to compare the two treatment regimens with respect to burden on healthcare  
571 provider's time.

572

573

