**STATISTICAL CONSIDERATIONS:**

**Sample Size Calculation**

We propose to test a non-inferiority hypothesis comparing the 6-month change from baseline in HbA1c between the two treatment groups, with a non-inferiority margin of 0.4%. We conservatively estimate the standard deviation of the difference at 0.5% based on results from reported studies with similar design[44, 45, 47]. Using a one-sided alpha of 0.025, we determine that 44 subjects per group completing 6 months will provide power 0.96 to test this non-inferiority hypothesis, shown below amongst with other scenarios (Hintze, J. (2011). PASS 11. NCSS, LLC. Kaysville, Utah, USA. [www.ncss.com](http://www.ncss.com)). We will need to randomize 100 patients to test this hypothesis assuming a 12% drop-out rate (estimated drop-out rate based on our extensive prior experience with similar population and length of study). We plan to screen 120 patients to account for approximately 20% anticipated screen failures.

Power and sample size estimation for Non-Inferiority Test (H0: Diff >= NIM;  
H1: Diff < NIM)  
Higher Means are Worse  
Test Statistic: T-Test

Power	N1/N2	Non-Inferiority Margin (NIM)	Actual Difference (D)	Significance Level (Alpha)	Beta	Standard Deviation1 (SD1)
1.000	44/44	0.4	0	0.025	0.000	0.3
1.000	48/48	0.4	0	0.025	0.000	0.3
1.000	50/50	0.4	0	0.025	0.000	0.3
0.960	44/44	0.4	0	0.025	0.040	0.5
0.973	48/48	0.4	0	0.025	0.028	0.5
0.977	50/50	0.4	0	0.025	0.023	0.5
0.755	44/44	0.4	0	0.025	0.245	0.7
0.791	48/48	0.4	0	0.025	0.209	0.7
0.808	50/50	0.4	0	0.025	0.192	0.7

Further, this sample size will yield at least 80% power at two-sided alpha=0.05, superiority hypothesis, for the secondary composite outcome endpoint of HbA1c<7% with no hypoglycemia and no significant weight gain, expecting that 25% and 5% reach

726 this endpoint with liraglutide treatment and standard basal-bolus insulin treatment,  
727 respectively.

728

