764 will be used to compare the pre-specified “treatment failure” end-point between groups.  
765 Safety endpoints and hypoglycemic and other adverse events will summarize in detail  
766 with descriptive statistics. The analysis of safety data will be performed for the ITT  
767 population.

768 Model assumptions regarding normality and covariance structure will be carefully  
769 assessed. Nonparametric tests or data transformations will be used if necessary to meet  
770 assumptions. Statistical analysis will be performed with SAS software (SAS Institute,  
771 Cary NC), particularly Proc Mixed for linear models with both fixed and random effects.

772 A two-sided alpha <5% will be considered significant for all analyses.

773

774 **Interim Analysis**

775 No interim analysis is planned.

776

777 **DATA HANDLING AND RECORD KEEPING:**

778 All data will be collected in strict compliance with the University's HIPPA rules.

779 Research records (source documents) will be kept in a double-locked filing system in a  
780 secure locked room. Collected data will be stored in an electronic study database will be  
781 encrypted and password protected and saved on the University's secure network. Only  
782 study personnel will have access to these records.

783

784 The institutional review board (IRB) governing this study may inspect the medical  
785 records of any patient involved in this study at any time.

786

787 Laboratory specimens will be collected under standard of care protocol at Parkland  
788 hospital laboratory and handled in accordance with the hospital policy.

789

790 The study blind will be maintained by the designated statistician and only broken by  
791 request from a treating physician in case of a medical emergency.

792

793 **ETHICS:**

794 Ethical Considerations:

795 1. Exclusion of non-English speakers- while translators are available during working  
796 hours, the investigators are worried that no translator will be available to assure  
797 safety measures at all times.

798 2. Compliance with Insulin Regimen- At times patients are not compliant with  
799 complicated insulin regimens and providers often continue to uptitrate insulin  
800 dosage when patients remain above HbA1c goal. If patient compliance improves  
801 once enrolled in the study, there is a higher risk of hypoglycemia. Every effort  
802 will be made at all visits to determine exactly what amount of insulin the patient  

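### No pre-randomisation cost window or baseline-cost covariate is specified for the two cost outcomes, although the planned record query could supply both; the gain is modest and depends on an unknown correlation

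*Combined protocol and SAP*

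**What the plan says.** Cost is in the study title, is the fourth specific aim, and supplies secondary outcomes 13 (total) and 14 (diabetes-related). The fourth aim covers inpatient and outpatient cost, whether or not related to diabetes.

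- **Data source.** Under Other Assessments, at the end of the study the EPIC "record system will be queried for the data regarding all healthcare related expenditures". No start date is given. The visit table marks cost extraction once, at visit 6, while the quality-of-life questionnaires are marked at visits 2 and 6.
- **Availability.** The Rationale for Study Location calls PHHS the ideal "location to conduct this study, as all patient-related information is captured and can be" queried at several levels, cost among them. The Background describes the hospital as a closed system. An inclusion criterion is "Currently receiving medical care at Parkland Health and Hospital System (PHHS"), with no minimum time in that system.
- **Analysis.** The only cost-specific analysis in the Statistical Analysis Plan is cost-effectiveness ratios with 95% intervals that allow for skewness, plus sensitivity analyses. No covariate is named. Baseline covariates appear only in logistic models of treatment efficacy.
- **General statements.** The Randomization (visit 2) section promises a baseline assessment of every outcome. The Statistical Analysis Plan sends continuous secondary outcomes to a repeated-measures mixed model of group comparisons and change since baseline. Neither mentions cost.

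**The concern.** Cost data are usually skewed, and the trial is sized for HbA1c. With about 44 completers per arm, a few expensive patients falling in one arm by chance can move the cost comparison. A patient's cost before randomisation cannot be affected by treatment and may predict later cost, particularly the non-diabetes part of outcome 13. If it can be had by widening the date range of a query that is planned anyway, leaving it out gives up precision for almost no saving.

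The form of adjustment also matters. If the general wording on change since baseline were applied to cost, it would suggest subtracting prior cost, which can be less precise than no adjustment at all.

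**Working it through.** **The plan's own figures.** The Sample Size Calculation section proposes to test "with a non-inferiority margin of 0.4"%, with SD 0.5%, and states: "Using a one-sided alpha of 0.025, we determine that 44 subjects per group completing 6 months will provide power 0.96". With 86 degrees of freedom, the noncentrality is 0.4 / (0.5 × √(2/44)) = 0.4 / (0.5 × 0.2132) = 3.75, and the noncentral t gives power 0.960. Dropout: 44 × 2 / (1 − 0.12) = 88 / 0.88 = 100. Both reproduce. The documents give no SD, power or detectable difference for cost, so there is no cost figure to reproduce.

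**Inputs for cost.** 44 per arm and two-sided 5% come from the plan. The coefficient of variation (CV) of cost and the within-arm correlation r between prior and study-period cost are assumptions.

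**Unadjusted interval.** The half-width for the difference in mean cost, as a share of the mean, is 1.99 × CV × √(2/44) = 0.424 × CV. That is 42% at CV 1.0 and 85% at CV 2.0. If cost is available for all 100 randomised patients, it is 1.984 × √(2/50) = 0.397 × CV, or 40% to 79%.

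**Two ways to use prior cost**, each relative to the unadjusted half-width:

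- Covariate: multiply by √(1 − r²). The same precision without the covariate would need 88 / (1 − r²) completers.
- Change score, with equal variances before and after: multiply by √(2(1 − r)).

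| Assumed r | Covariate factor | Interval narrower by | Equivalent completers | Change-score factor |
|---|---|---|---|---|
| 0.2 | 0.980 | 2.0% | 92 | 1.265 (26% wider) |
| 0.3 | 0.954 | 4.6% | 97 | 1.183 (18% wider) |
| 0.5 | 0.866 | 13.4% | 117 | 1.000 (no gain) |
| 0.6 | 0.800 | 20.0% | 138 | 0.894 (11% narrower) |

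The change score loses to no adjustment when 2(1 − r) > 1, that is, r < 0.5. It is also never better than the covariate, because 2(1 − r) − (1 − r²) = (1 − r)², which cannot be negative.

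**Cost of the extra term.** One covariate multiplies the half-width by about √(1 + 1/84) = 1.006. The net gain is then 1.4% at r = 0.2 and 4.0% at r = 0.3, and about zero at r = 0.1.

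**Incomplete history.** Suppose a fraction m of patients, unrelated to their cost, has prior cost recorded as zero. The correlation falls to r × √((1 − m) / (1 + m/CV²)). With m = 0.30 and CV = 1 (both assumed), the multiplier is √(0.70/1.30) = 0.734. Then r = 0.3 becomes 0.22 and the gain falls from 4.6% to 2.5%; r = 0.6 becomes 0.44 and the gain falls from 20% to 10%. A simulation with lognormal costs showed a similar loss, from about 6% to 3% and from 22% to 12%.

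**The case against.** The strongest reply is that silence is not a decision. The query has no start date, so the time at which it is run does not fix the period it covers. The plan also promises a baseline for every outcome and an analysis of change for continuous secondary outcomes, and cost is one of these. A reader might infer that the sponsor chose to compare costs without prior cost. The documents do not support that; they support only that no window and no covariate are specified. The general sentences still do not fill the gap. Cost accrues over time, so a baseline taken at a single visit has no meaning until a look-back is defined, and the cost row of the visit table is blank at visit 2.

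A reader might also infer that cost is among the least precise outcomes. That cannot be checked, because no cost variance is given.

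The objection that r may be low stands. The exclusions remove patients needing admission, those with serious or unstable conditions and those with planned surgery, and prior cost might have predicted later cost best in such patients. Emergency-room recruits may bring a one-off visit into the look-back. For outcome 14, recent prandial insulin, GLP-1 analogues and DPP-4 inhibitors are excluded and every patient starts detemir, so earlier diabetes cost reflects a different regimen. A new admission during follow-up may not be foreshadowed by prior cost at all.

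**Conclusion.** The point holds as a missed efficiency for two secondary outcomes. The plan specifies neither a pre-randomisation cost window nor a baseline-cost covariate, although its own description of the record system implies that prior cost could be retrieved.

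The likely size is a 95% interval 2% to 20% narrower for an assumed r of 0.2 to 0.6. The lower part of that range is quite possible here, given the exclusions and patients with short histories. Even at r = 0.5 the half-width stays wide: 42% × 0.866 = 37% of mean cost at CV 1, and 85% × 0.866 = 74% at CV 2.

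A reader might infer that the unadjusted cost comparison is biased. It is not: randomisation protects it, and the primary HbA1c analysis is untouched. The change is optional but cheap. It should be fixed before cost data are seen, because a look-back chosen afterwards on skewed data would invite doubt.

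**What to change.** 1. State the follow-up cost period, and extend the same EPIC query to a fixed look-back, for example the 6 months before randomisation. Say whether an emergency-room visit that led to recruitment counts in it.
2. Pre-specify prior total cost as a covariate for outcome 13 and prior diabetes-related cost for outcome 14, in the between-arm comparison of cost. State that it is a covariate and not a change score.
3. Use an interval robust to skewness, such as a bootstrap that resamples patients within arm.
4. Use the adjusted cost difference as the cost component of the cost-effectiveness ratio, so that the ratio and the cost comparison agree.
5. Report how many patients have little or no recorded cost in the look-back.

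This costs a wider date range in one query, one model term and a few sentences in the Statistical Analysis Plan. It needs no extra visit or patient burden. The downside is little gain if r is low: near r = 0 the interval would be about 0.6% wider.

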## 574 **RISKS ASSOCIATED WITH THE PARTICIPATION IN THE STUDY:**

### 575 Risks of Liraglutide:

576

577 Very common (reported by more than 10 percent of the patients):

578

- - Gastrointestinal adverse events are the most common side effect of liraglutide and reported in up to 41% of patients. Nausea is seen in approximately 13% of patients treated with liraglutide and is usually developed in the first 2 weeks. It tends to be mild, dose-related and decline over time. In some patients the nausea can be more severe and be associated with vomiting which is usually transient and self-resolving.

583

584

585

Common (reported by 5-10 percent of the patients)

586

- Low blood sugar (hypoglycemia) - - The risk of having hypoglycemia with liraglutide is higher if taking it with another medicine that can cause hypoglycemia, such as a sulfonylurea or insulin. In some people, the blood glucose may get so low that they need another person to help them. The dose of your sulfonylurea medicine or insulin may need to be lowered while using liraglutide.
- Headache and upper respiratory tract infections have been reported in 7-9% of patients treated with liraglutide. A similar percentage of patients developed headaches with placebo or comparator drug.

594

595

596

Uncommon side effects (reported by 1-5 percent of the patients):

597

- Injection site reactions (e.g., injection site rash, erythema) were reported in approximately 2% of liraglutide treated patients in the five clinical trials of at least 26 weeks duration. Less than 0.2% of liraglutide-treated patients discontinued due to injection site reactions.

600

601

602

Very rare side effects (affects less than 1 percent of patients)

603

- Acute pancreatitis (inflammation of the pancreas) - there have been few reported event of acute pancreatitis presenting with persistent severe abdominal pain (usually accompanied by vomiting). Patients experiencing the above symptoms should contact the study doctor who will decide on whether they should discontinue the trial medication and /or require additional diagnostic procedures.
- Rarely, a severe form of allergic reaction (anaphylactic reaction) with additional symptoms such as breathing problems, swelling of throat and face, fast heart beat

609

610 etc. has been reported with marketed use of Liraglutide. Patients experiencing  
611 these symptoms should seek immediate medical help and inform the trial doctor  
612 as soon as possible.

- 613 • Kidney failure – Liraglutide may cause nausea, vomiting or diarrhea, leading to  
614 loss of fluids (dehydration). Dehydration may cause kidney failure which can  
615 lead to the need for dialysis. This can happen in people who have never had  
616 kidney problems before. Drinking plenty of fluids may reduce the risk of  
617 dehydration.

618

619 Other potential risks related to liraglutide:

- 620 • Hyperglycemia (too high blood glucose) can occur, especially if there is  
621 insufficient treatment. . The symptoms of hyperglycemia include increased  
622 urination, feeling thirsty, losing appetite, feeling sick (nausea or vomiting),  
623 feeling drowsy or tired, flushed, dry skin, dry mouth and a fruity (acetone) smell  
624 of the breath. If not treated, these symptoms may develop into a serious condition  
625 called diabetic ketoacidosis which may even lead to death.
- 626 • Thyroid tumors, including cancer -During the drug testing process, the medicine  
627 in Victoza caused rats and mice to develop tumors of the thyroid gland. Some of  
628 these tumors were cancers. It is not known if Victoza will cause thyroid tumors  
629 or a type of thyroid cancer called medullary thyroid cancer in people. If  
630 medullary thyroid cancer occurs, it may lead to death if not detected and treated  
631 early. If you develop tumors or cancer of the thyroid, your thyroid may have to  
632 be surgically removed. Fibrosarcomas (cancer underneath the skin) were seen at  
633 the point of injection (skin) in male mice that underwent a 2 year study of  
634 liraglutide. These fibrosarcomas were attributed to the high local concentration  
635 of drug near the injection site. The liraglutide concentration in the preparation  
636 used for humans is 10 times higher than the concentration used in mice. It is not  
637 known if liraglutide will cause fibrosarcomas in people.

638

639 Risk of insulin detemir and aspart:

640

641 Very common (1-10 in 100 patients):

- 642 • Hypoglycemia (low blood sugar) is the most common adverse reaction of insulin  
643 therapy and may be life- threatening if severe and not treated appropriately.
- 644 • Mild-moderate weight gain is expected with any insulin therapy

645

646 Less common (less than 1 in 100 patients):

- 647 • Severe, life-threatening, generalized allergy, including anaphylaxis, can occur  
648 with any insulin products, including detemir insulin or aspart insulin.
- 649 • Other adverse reactions associated with detemir insulin and/or aspart insulin  
650 include injection site reactions, lipohypertrophy, rash, itching.
- 651 • Needles and insulin pens should never be shared.

652

653 Risk of Metformin:

654

655 Very common (1-10 in 100 patients):

- 656 • Abdominal or stomach discomfort
- 657 • Decreased appetite
- 658 • Diarrhea
- 659 • Bloating
- 660 • Low serum Vitamin B12 levels without clinical manifestations

661

662 Precautions:

- 663 • Lactic Acidosis: Lactic acidosis is a very rare, but serious, metabolic complication  
664 that can occur due to Metformin accumulation during treatment with Metformin  
665 HCl; when it occurs, it is fatal in approximately 50% of cases. Lactic acidosis  
666 may also occur in association with a number of pathophysiologic conditions,  
667 including diabetes mellitus. Metformin should be discontinued immediately and  
668 health care provider should be promptly notified if unexplained increase in  
669 breathing rate, muscle aches, fatigue and unusual somnolence occur.
- 670 • Patients with Renal disease or renal dysfunction (e.g., as suggested by eGRF <30  
671 ml/min) should not use metformin
- 672 • Metformin should be temporarily discontinued 48h prior to radiologic studies  
673 involving intravascular administration of iodinated contrast materials 48h prior to  
674 procedure to avoid increased risk of development of lactic acidosis and restarted  
675 24h after the procedure.
- 676 • Excessive alcohol intake, either acute or chronic should be avoided while  
677 receiving Metformin.

678

679 **SAFEGUARDS AND PRECAUTIONS TO MINIMIZE RISKS/HARMS:**

- 680 • Hypoglycaemia episodes will very closely monitored through the study using self-  
681 glucose monitoring. Review of blood glucose diary and hypoglycaemic events  
682 will be discussed during office, phone visits and as needed. Patient will be  
683 instructed during randomization visit on how to properly handle mild, moderate and  
684 severe hypoglycemic episodes and how to reduce their basal insulin doses  
685 according to study protocol. Those instructions will be reinforced as needed  
686 during the study.
- 687
- 688 • Should any patients randomized to liraglutide treatment experience persistent  
689 hyperglycemia (defined as Hb1c>10%) at the 3-mo visit (visit 5), meal-time  
690 insulin aspart will be initiated per the same protocol as the standard group
- 691
- 692 • Should any patients randomized to the “standard of care” group experience  
693 persistent hyperglycemia (defined as HbA1c>10%) at the 3-mo visit (visit 5),  
694 treatment and insulin titration will continue as scheduled.
- 695
- 696 • Patients will be monitored closely for any drug-related side effects. They will be  
697 provided with instruction on when to call the PI and a direct phone line, so they  
698 can immediately report any problems or concerns. Instructions will be given on  
699 possible side effects and how to avert/minimize them.

700

- Only qualified personnel will perform blood draws to minimize the risk of complications.
- Patients are allowed to skip questions on the questionnaire should they feel that the question might pose a psychological burden.

**STATISTICAL CONSIDERATIONS:**

**Sample Size Calculation**

We propose to test a non-inferiority hypothesis comparing the 6-month change from baseline in HbA1c between the two treatment groups, with a non-inferiority margin of 0.4%. We conservatively estimate the standard deviation of the difference at 0.5% based on results from reported studies with similar design[44, 45, 47]. Using a one-sided alpha of 0.025, we determine that 44 subjects per group completing 6 months will provide power 0.96 to test this non-inferiority hypothesis, shown below amongst with other scenarios (Hintze, J. (2011). PASS 11. NCSS, LLC. Kaysville, Utah, USA. [www.ncss.com](http://www.ncss.com)). We will need to randomize 100 patients to test this hypothesis assuming a 12% drop-out rate (estimated drop-out rate based on our extensive prior experience with similar population and length of study). We plan to screen 120 patients to account for approximately 20% anticipated screen failures.

Power and sample size estimation for Non-Inferiority Test (H0: Diff >= NIM;  
H1: Diff < NIM)  
Higher Means are Worse  
Test Statistic: T-Test

Power	N1/N2	Non-Inferiority Margin (NIM)	Actual Difference (D)	Significance Level (Alpha)	Beta	Standard Deviation1 (SD1)
1.000	44/44	0.4	0	0.025	0.000	0.3
1.000	48/48	0.4	0	0.025	0.000	0.3
1.000	50/50	0.4	0	0.025	0.000	0.3
0.960	44/44	0.4	0	0.025	0.040	0.5
0.973	48/48	0.4	0	0.025	0.028	0.5
0.977	50/50	0.4	0	0.025	0.023	0.5
0.755	44/44	0.4	0	0.025	0.245	0.7
0.791	48/48	0.4	0	0.025	0.209	0.7
0.808	50/50	0.4	0	0.025	0.192	0.7

Further, this sample size will yield at least 80% power at two-sided alpha=0.05, superiority hypothesis, for the secondary composite outcome endpoint of HbA1c<7% with no hypoglycemia and no significant weight gain, expecting that 25% and 5% reach

726 this endpoint with liraglutide treatment and standard basal-bolus insulin treatment,  
727 respectively.

728

